### **9.3. Response criteria**

- Numbering of weeks/timing of events

Week 1 is the week corresponding to the first infusion of ATO. Weeks are counted from this week onwards, unless stated to the contrary. Investigators should take care not to confuse weeks post-ATO with weeks post-transplantation.

➤ Response to the study regimens:

- Assessment of response (CR vs. PR): The main issue in chronic GvHD is the lack of consensus criteria for the assessment of the response. In 2015 an NIH sponsored meeting was held with a panel of experts on chronic GvHD. Their proposal for grading of chronic GvHD will be used in this protocol (see Appendix 1).
- The following definitions will be used:
- Complete remission (CR) is defined as complete disappearance of any sign of chronic GvHD
- Partial remission (PR) is defined as improvement of 1 or more point on a 4 to 7-point scale or an improvement of 2 or more points on a 10 to 12-points scale in at least 1 organ or site without progression in any other organ or site. For patients with BOS, an absolute improvement in %FEV1 of 10% predicted or more (eg, 50% to 60%) is considered a PR as long as the initial % FEV1 is < 70%. Normalization ( $\geq 80\%$ ) is considered a CR.
- Progressive disease (PD) is defined as at least one organ system has worsened by at least one stage without improvement of any other organ systems from baseline
- For skin, eye, esophagus, and upper and lower GI tract, a worsening of 1 point or more on the 0 to 3 scale is considered progression, except a change from 0 to 1, which is considered trivial progression since it often reflects mild, nonspecific, intermittent, self-limited symptoms and signs that do not warrant a change of therapy.
- For joint/fascia, a worsening of 1 point or more on the 0 to 3 scale is considered progression, even if from 0 to 1, because a change to score 1 was considered meaningful progression that would prompt a change in therapy. For joints assessed by the photographic range of motion, a worsening of 1 or more points for the 7-point scales and 1 or more points for the 4-point scale is considered progression.

- For mouth, a worsening of 2 or more points on the 1-point scale indicates progression.
- Worsening of liver GvHD is defined by an increase of 2 or more times the upper limit of normal for the assay for alanine transaminase, alkaline phosphatase, or total bilirubin.

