17. APPENDICES

17.1 RESPONSE CALCULATION ALGORITHM

Etude GMED_16_001 : Evaluation des réponses complètes et partielles – 19/10/2020

Les réponses sont définies comme (règles de calcul basées sur le protocole et l'article Lee et al)

- Complete response at a visit: Lorsque tous les scores de « cGVHD activity assessment form A » des organes suivants sont à 0 ou que la variable "abnormalities present but explained entirely by non-GVHD documented cause » soit égale à Oui.

Détails :

Si une valeur est manquante pour un des organes atteints lors de la visite V1, la réponse ne peut pas être considérée comme complète. le fait que la valeur est manquante sera documentée.

Si une valeur à la visite d'intérêt est manquante sur un organe non atteint lors de la visite V1, la réponse complète peut être établie, car les réponses complètes ou partielles ne sont établies que sur les organes atteints à V1.

Si « abnormalities present but explained entirely by non-GVHD documented cause » = Oui pour un organe à la visite considérée, le score de cet organe n'est pas corrigé et cet organe n'est pas considéré pour l'évaluation de la réponse complète. cela ne créera pas de valeur manquante pour cet organe et n'empêchera pas la réponse d'être considérée comme complète si les informations sur les autres organes sont disponibles.

- BSA=0 ET skin features=0

M6_GVHD_A_S (préfixe M6 ou C1W6, W14, M9 et M12 selon la visite considérée)

M6_GVHD_A_S_F_S

M6_GVHD_A_S_ABN

- Eyes=0

M6_GVHD_A_E

M6_GVHD_A_E_ABN

- Gastrointestinal=0 (pour chacun des 3 scores : Gastro-oesophageal, Gastro-upper, Gastro-lower)

M6_GVHD_A_GASTRO1

M6_GVHD_A_GASTRO2

M6_GVHD_A_GASTRO3

M6_GVHD_GAST_ABN

- Mouth=0 (considérer la somme des 3 scores : Erythema, Lichenoid, Ulcers)

M6_GVHD_A_MOUTH1
 M6_GVHD_A_MOUTH2
 M6_GVHD_A_MOUTH3
 M6_GVHD_MTH_ABN

Joint and fascia =0

M6_GVHD_A_J
 M6_GVHD_A_J_ABN

Liver : les 3 valeurs (Bilirubine, ALAT et PAL) sont en dessous des ULN (Unité limite supérieure) si le score hépatique était >0 à V1 (table 1 et annexe du protocole)

.<M6_GVHD_A_L_SGPT_V<=M6_GVHD_A_L_SGPT_U_V
 .<M6_GVHD_A_L_ALK_V<=M6_GVHD_A_L_ALK_U_V
 M6_GVHD_LIV_ABN

Le score à V1 est calculé comme :

Score = 0 : Bilirubine normale WITH ALAT AND PAL < 3 UNL

(.<V1_GVHD_A_L_BILI_V<=V1_GVHD_A_L_BILI_U_V et
 .<V1_GVHD_A_L_SGPT_V<3* V1_GVHD_A_L_SGPT_U_V et
 .<V1_GVHD_A_L_ALK_V<3* V1_GVHD_A_L_ALK_U_V)

Score = 1 : Bilirubine normale WITH 3 UNL<=ALAT < 5 UNL AND 3 UNL <=PAL<5 UNL

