Score = 2 : Bilirubine élevée (>1*ULN) mais <= à 3 mg/dL OR ALAT >= 5 UNL OR PAL >=5 UNL (non mentionné dans article NIH).

Score = 3 : Bilirubine élevée > à 3 mg/dL

Lung : si FEV1 >=80% et FEV1<70 à V1. et dans le cas où la valeur de FEV1 est manquante, si le score est égal à 0

M6_GVHD_A_LU_FEV1_V>= 80
 missing(M6_GVHD_A_LU_FEV1_V) and M6_GVHD_A_L=0
 M6_GVHD_A_L
 M6_GVHD_A_L_ABN

Calcul de réponse par organe :

Aucun calcul de réponse **par organe** (complète, partielle ou progression) n'est effectué si :

- « abnormalities present but explained entirely by non-GVHD documented cause » = Oui pour un organe à la visite considérée
- CR_*organe*, PR_*organe* et PD_*organe* sont alors mis à . (manquant)

Aucun calcul de réponse complète ou partielle **par organe** n'est effectué si :

- l'organe n'est pas atteint à V1 ou abnormalities present but explained entirely by non-GVHD documented cause » = Oui pour un organe à la visite V1.
- la progression est recherchée même si pas d'atteinte à V1
- CR_*organe* et PR_*organe* sont alors mis à . (manquant)

- **Partial response by organ:** en se basant sur les mêmes scores et en s'intéressant aux diminutions (ou augmentations) entre V1 (mêmes variables qu'indiquées précédemment mais qui commencent par « V1 » au lieu de « M6 ») et la visite considérée (M6, W6, W14, M9 ou M12)

- une diminution d'1 point pour les scores sur des échelles de 0 à 4 pour : Skin BSA, Skin features, Eyes, Joints, Gastro-oesophageal, Gastro-upper, Gastro-lower,
- une diminution de 2 points pour la somme des 3 sous-scores pour Mouth
- pour Lung, une augmentation entre V1 et la visite d'au moins 10% sur FEV1 avec FEV1 à V1 <70. Dans le cas de FEV1 manquants à V1 et ou M6, une diminution d'1 point sur le score 'lungs'
- pour Liver, (Bilirubine, ALAT ou PAL),
- si les valeurs à M6 sont en dessous des normales, la réponse est considérée Complète
- sinon la recherche d'une réponse partielle est effectuée : diminution de 50% de la valeur initiale
 Le ratio est calculé ainsi : $(M6-V1/V1)*100$ et si le ratio est inférieur à -50 (mais pas de progression pour une des autres valeurs), il y a une réponse partielle

Global Partial response: au moins une réponse partielle sur un organe et avec une absence de progression pour un autre site

- **Progressive disease by organ:**

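### SAP 17.1 builds global partial response only from organ-level partial responses, so a patient whose liver normalises while another involved organ is unresolved can be computed as a non-responder

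*SAP*

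**What the plan says.** The algorithm in SAP 17.1 sets these rules:

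- **Global CR:** "Lorsque tous les scores de « cGVHD activity assessment form A » des organes suivants sont à 0", or the abnormality is attributed to a documented non-GvHD cause. One unresolved organ therefore rules out global CR.
- **Global PR:** "au moins une réponse partielle sur un organe et avec une absence de progression" at another site. Organ-level CR is not mentioned.
- **Liver:** "si les valeurs à M6 sont en dessous des normales, la réponse est considérée Complète", and on the next line "sinon la recherche d'une réponse partielle est effectuée : diminution de 50% de la valeur initiale". The SAP expresses this fall as a relative change below −50%.
- **Mouth:** CR is "Mouth=0 (considérer la somme des 3 scores : Erythema, Lichenoid, Ulcers"), while PR is "une diminution de 2 points pour la somme des 3 sous-scores pour Mouth".
- **Mixed response:** progression in one organ together with a partial response in another. Organ-level CR is again absent.

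Protocol 9.3 defines PR as improvement past a stated threshold "in at least 1 organ or site without progression in any other organ or site". Its mixed response counts either CR or PR in an organ. Protocol Table 4 gives liver PR as a 50% decrease and liver CR as normal values. SAP 8.2.1 repeats the protocol's PR definition and the organ table.

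SAP 11.4.1.1 bases the main analysis on the response judged by the investigator. The computed 6-month response is used in sensitivity analyses b and d of SAP 11.4.1.2.

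**The concern.** An organ that recovers fully should never leave the patient with a worse overall classification than an organ that recovers in part. Under 17.1 it can.

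The computed response is the planned rule-based check on an investigator-judged endpoint in a study with no randomisation and no blinding. It fills 16 planned tables: 14.2.2.3 to 14.2.2.16, 14.2.2.19 and 14.2.2.20. If the algorithm discards genuine responders, the computed rate falls below the investigator's rate, and a reader may put down to generous judgement a gap that the rule itself created.

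**Working it through.** **1. The rules applied literally.** The values below were chosen for illustration; the thresholds are those of SAP 17.1. Liver values are multiples of ULN, bilirubin is normal throughout, and organs not listed are uninvolved.

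| Baseline to month 6 | 17.1 as written | Corrected rule |
|---|---|---|
| ALT 6 to 0.8, ALP 4 to 0.8; skin 2 to 2 | no response | PR |
| ALT 6 to 2.4, ALP 4 to 1.5; skin 2 to 2 | PR | PR |
| Mouth 1 to 0; skin 2 to 2 | no response | PR |
| Mouth 2 to 0; skin 2 to 2 | PR | PR |
| Eyes 1 to 0; skin 2 to 2 | PR | PR |
| Liver the only involved organ, normalises | CR | CR |
| Mouth the only involved organ, 1 to 0 | CR | CR |
| Liver normalises; skin 2 to 2; joints 0 to 1 | progression | mixed |

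Rows 1 and 2 show the inversion. In row 2 the relative changes are (2.4 − 6)/6 = −60% and (1.5 − 4)/4 = −62.5%, so the liver is in PR and so is the patient. In row 1 the ALT change is larger, (0.8 − 6)/6 = −87%. But the liver is classed CR, the PR search is skipped, and no PR flag remains to feed the global rule. The unresolved skin blocks global CR.

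**2. Comparison with the protocol.** By the SAP's liver score, a liver involved through its enzymes starts at 3 × ULN or more. Reaching 1 × ULN or less means a fall of at least (3 − 1)/3 = 67%, which passes Table 4's 50% threshold. Under protocol 9.3 such a patient, with nothing progressing, is in PR. A liver involved only through mildly raised bilirubin is less clear: 1.5 to 1.0 × ULN is normalisation but a fall of only 33%. It then stands where mouth 1 to 0 stands, as an organ CR in Table 4 that does not reach the PR threshold.

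**3. Which organs are exposed.** Skin, eyes, joints and the three GI scores have a 1-point PR threshold, so a fall to 0 also meets PR. Lung CR requires FEV1 to go from below 70% to at least 80%, which also passes the 10% PR rise. Only the liver, and mouth 1 to 0, can reach CR without a PR flag.

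**4. Scale.** The plan's design reproduces: with n = 21 and 17 successes required, P(X ≥ 17 | 0.60) = 0.0370 and P(X ≥ 17 | 0.85) = 0.8025; 21/0.9 = 23.3, rounded up to 24. One patient is 1/21 = 4.8 points, or 1/24 = 4.2 points.

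The documents give no share of responders who would be lost. As an assumed range, losing a share m of true responders turns 85% into 85% × (1 − m):

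| Assumed m | Computed rate | P(X ≥ 17 of 21) |
|---|---|---|
| 0 | 85.0% | 80.3% |
| 2% | 83.3% | 73.4% |
| 5% | 80.8% | 62.0% |
| 10% | 76.5% | 42.9% |

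This is a yardstick only. Sensitivity analyses b and d take their method from 11.4.1.1, which compares the lower limit of a two-sided 95% Clopper-Pearson interval with 60% in the FAS. For that limit to exceed 60% with 21 patients, 18 responders are needed: P(X ≥ 18 | 0.60) = 0.0110 is below 0.025, while 0.0370 for 17 is not. The FAS need not number 21.

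**The case against.** **A benign reading exists.** 17.1 says that its rules follow the protocol, and the French could be taken loosely as a partial response or better. This does not survive the mixed-response line, which also names only partial response where protocol 9.3 names CR or PR. A programmer following the text would omit CR in both places.

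**The situation is narrow.** The liver must be involved at baseline and normalise, another involved organ must remain unresolved, no organ may be in PR, and none may progress. That is correct, and the frequency is unknown. It limits the size of the problem but does not remove it.

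**Mouth 1 to 0 is not clearly against the protocol.** Protocol 9.2 scores the mouth from 0 to 12, and the PR text asks for 2 or more points on a scale of that length. Table 4 calls a score of 0 a complete organ response, but no sentence says that an organ CR below the PR threshold makes a global PR. This objection stands, so the liver case carries the point.

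**A reader might infer that every organ CR is lost**, because the table in SAP 11.4.2.1 lists CR and PR as separate rows. If the flags were coded as exclusive, eyes 1 to 0 with skin unchanged would indeed become a non-response. But 17.1 names separate CR, PR and progression flags and makes them exclusive only for the liver. The 11.4.2.1 table is a display layout. The documents do not support the wider claim.

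**Conclusion.** The point holds for the computed response. As written, 17.1 classes a normalised liver with another involved organ unresolved as no response, while a partial fall of more than 50% is a response. This conflicts with protocol 9.3, protocol Table 4 and SAP 8.2.1. The error runs one way: every patient classed PR as written stays PR under the corrected rule, so the computed rate can only be too low.

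A reader might infer that the trial's conclusion, or the 17-of-21 cut-off, is at risk. It is not: the main analysis uses the investigator's judgement. Response by organ uses the organ flags, and the SAP's progression-free survival uses progression at any site, so neither changes. What is affected is the credibility of sensitivity analyses b and d, by 4.8 points per patient if 21 are analysed. The number of such patients cannot be known from the documents, and the percentages lost in the working are assumptions. This is a minor but real drafting error.

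**What to change.** Change two rules in SAP 17.1:

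- Global PR: at least one organ with CR or PR, no progression in any other organ, and not global CR.
- Mixed response: CR or PR in at least one organ with progression in another, as in protocol 9.3.

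State that, under the new wording, mouth 1 to 0 and a mild bilirubin elevation that normalises count towards global PR. For these cases the edit goes somewhat beyond the protocol's PR thresholds, so the choice should be deliberate.

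Among the test patients, only the liver and mouth 1-to-0 cases change to PR, and one progression case becomes mixed (a non-response either way). The cost is a few words in two rules and the matching lines of code, plus a rerun of the computed-response tables if they already exist. Sample size, data collection and the main analysis do not change. The algorithm is dated 19 October 2020 and the SAP synopsis places database lock in December 2020, so on the SAP's own calendar the correction could be made before lock.

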- For patients with lung involvement, absolute worsening of FEV1 by 10% predicted or more (eg, 50% to 40%) is considered progression, as long as the final %FEV1 is < 65% (because initial %FEV1 must be < 75% to establish the diagnosis of lung involvement). If PFTs are not available, then worsening of the clinical lung score based on symptoms by 1 or more points should be scored as progression, except from score 0 to 1, which is considered trivial progression because of its lack of specificity for lung chronic GvHD.
- Mixed response is defined as CR or PR in at least one organ accompanied by progression in another organ
- Unchanged: outcome that does not meet criteria for CR, PR, PF or mixed response are considered unchanged
- Resistance is defined as lack of a CR/PR 2 weeks after the last ATO infusion, requirement for alternative therapy or death from GvHD before the last ATO infusion
- Failure is defined as death, recurrent or progressive malignancy or the initiation of new systemic treatment for chronic GvHD increased dosing of existing treatment will not be considered as failure

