11.4.2.2 Survival analyses

a) Failure free survival

A survival analysis will be conducted to describe the occurrence of failure between the first infusion of ATO and Vi, with Vi={M6;M12}.

Derivation

Derived variables	Definition
Failure at Vi Calculated at Vi={M6;M12}	Defined as death, recurrent or progressive malignancy, or the initiation of a new systemic treatment for chronic GvHD. Systemic treatment are: Methotrexate, Rapamune, TLI, Extracorporeal photopheresis, Rituximab, Jakavi, Glivec, Prograf, Imurel or other medications specified into the CRF (Vi_RESP_FAIL and or Vi_RESP_FAIL_S)
Time calculation from first ATO infusion to failure at Vi Calculated at Vi={M6;M12}	If the event appears: the difference of date between the first ATO infusion and the first failure (expressed in months) is calculated. The event will be not censored. $(\text{Date of first ATO infusion} - \text{Date of first failure})/30.5$ If the event does not appear, the difference of date between the first ATO infusion and Vi (expressed in months) is calculated. The event will be censored.

The following table will be presented at M6:

FAS Population

(N = XX)

First time of failure between first ATO infusion and M6 (in months)	n/M (%) of events	n/N (XX.XX%)
	n/M (%) of censored	n/N (XX.XX%)

The Kaplan-Meier survival estimates will be plotted with the number of subjects at risk and 95% confidence limits.

These analyses will be also presented at M12.

b) Progression free survival

A survival analysis will be conducted to describe the occurrence of progression between the first infusion of ATO and Vi, with Vi={M6;M12}.

Derivation

Derived variables	Definition
Progressive disease at Vi Calculated at Vi={M6;M12}	Global progressive disease as define in Appendix 17.1
Time calculation from first ATO infusion to failure at Vi Calculated at Vi={M6;M12}	If the event appears: the difference of date between the first ATO infusion and the first progression (expressed in months) is calculated. The event will be not censored. $(\text{Date of first ATO infusion} - \text{Date of first progression})/30.5$ If the event does not appear, the difference of date between the first ATO infusion and Vi (expressed in months) is calculated. The event will be censored.

The following table will be presented at M6:

FAS Population		
(N = XX)		
First time of progression between first ATO infusion and M6 (in months)	n/M (%) of events	n/N (XX.XX%)
	n/M (%) of censored	n/N (XX.XX%)

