- peau, yeux, œsophage, tractus gastro-intestinal supérieur et inférieur : augmentation 1 point ou plus sur échelle de 0 à 3 = progression SAUF si changement de 0 à 1 (progression non spécifique)
- Joint: augmentation d'1 point ou plus = progression
- bouche : changement de 2 points ou plus sur la somme des 3 sous-scores

- pour Lung, diminution de 10 % avec FEV1 à V1 < 75% . Dans le cas de FEV1 manquants, augmentation d'1 point ou plus *SAUF* si changement de 0 à 1 (progression non spécifique)

- pour Liver, si l'une des valeurs à M6 est au-dessus de la normale pour Bilirubine, ALAT ou PAL, la recherche d'une progression est effectuée : la différence M6 – V1 est calculée et si la différence est supérieure à 2*ULN, il y a Progression.

Global progressive disease : si au moins un site avec une progression

Mixed response: si **Progressive disease** sur au moins un organe et **Partial response** sur au moins un autre

Extraits du protocole :

Table 4. Response determination for chronic GvHD (extrait du protocole)

Organ	Complete Response	Partial Response	Progression
Skin	NIH Skin Score 0 after previous involvement	Decrease in NIH Skin Score by 1 or more points	Increase in NIH Skin Score by 1 or more points, except 0 to 1
Eyes	NIH Eye Score 0 after previous involvement	Decrease in NIH Eye Score by 1 or more points	Increase in NIH Eye Score by 1 or more points, except 0 to 1
Mouth	NIH Modified OMRS 0 after previous involvement	Decrease in NIH Modified OMRS of 2 or more points	Increase in NIH Modified OMRS of 2 or more points
Esophagus	NIH Esophagus Score 0 after previous involvement	Decrease in NIH Esophagus Score by 1 or more points	Increase in NIH Esophagus Score by 1 or more points, except 0 to 1
Upper GI	NIH Upper GI Score 0 after previous involvement	Decrease in NIH Upper GI Score by 1 or more points	Increase in NIH Upper GI Score by 1 or more points, except 0 to 1
Lower GI	NIH Lower GI Score 0 after previous involvement	Decrease in NIH Lower GI Score by 1 or more points	Increase in NIH Lower GI Score by 1 or more points, except from 0 to 1
Liver	Normal ALT, alkaline phosphatase, and Total bilirubin after previous elevation of 1 or more	Decrease by 50%	Increase by 2 × ULN

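### The SAP's lung-progression rule exempts every patient with a measured baseline FEV1 of 75% or more, against Table 4 and against the SAP's own statement that progression is sought without baseline involvement

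*SAP*

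**What the plan says.** **SAP 17.1, progressive disease by organ.** With FEV1 available, lung progression is "pour Lung, diminution de 10 % avec FEV1 à V1 < 75" (per cent). There is no condition on the follow-up value, and the text does not say whether the 10% is absolute or relative. If FEV1 is missing, the symptom score is used instead ("Dans le cas de FEV1 manquants, augmentation d'1 point ou plus"). A change from 0 to 1 is excluded, and baseline FEV1 plays no part.

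**SAP 17.1, response by organ.** For an organ not involved at V1, complete and partial response are not computed, but "la progression est recherchée même si pas d'atteinte à V1". SAP 11.4.2.1 makes the same exception for progressive disease.

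**Protocol 7.3.2.1 and 9.3.** "For patients with lung involvement, absolute worsening of FEV1 by 10% predicted or more (eg, 50% to 40%) is considered progression", and the rule continues "as long as the final %FEV1 is < 65% (because initial %FEV1 must be < 75% to establish the diagnosis of lung involvement".

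**Protocol Table 4**, reproduced in SAP 8.2.1 and 17.1. The lung progression cell asks for an absolute 10-point fall in %FEV1, with no threshold on the baseline or final value.

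**Protocol Appendix 2.** FEV1 of 60-79% is lung score 1. Table 3 places lung score 1 in moderate disease.

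**Use of the rule.** SAP 11.4.2.2 b takes as its event "Global progressive disease as define in Appendix 17.1", which is met by progression at any one site. SAP 11.4.2.1 uses the algorithm for each organ, and sensitivity analyses b and d in SAP 11.4.1.2 use the computed response. The main analysis in SAP 11.4.1.1 uses the investigator's judgement at month 6.

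**The concern.** The protocol text sets its lung threshold on the final FEV1; the SAP sets one on the baseline FEV1 instead. A baseline condition removes from assessment the patients in whom new lung disease could appear during follow-up, although the SAP says that new involvement is to be looked for.

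The classification consequence is direct. Under SAP 17.1 a global partial response needs improvement in one organ and no progression elsewhere. A patient whose skin improves while FEV1 falls from 90 to 45 would be a computed partial responder instead of a mixed response, and would be event-free for progression.

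In a single-arm, unblinded trial the computed response is the plan's check on investigator judgement. A rule that cannot see this kind of progression weakens that check.

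**Working it through.** Let b be baseline and f follow-up FEV1, both in % predicted.

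**1. The plan's own link between thresholds.** The protocol ties initial < 75% to final < 65%. This reproduces: 75 − 10 = 65, so b < 75 with b − f ≥ 10 implies f < 65.

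**2. The rules.**
- Protocol text: b − f ≥ 10 and f < 65, introduced as a rule for patients with lung involvement.
- Table 4: b − f ≥ 10.
- SAP 17.1, absolute reading: b − f ≥ 10 and b < 75.
- SAP 17.1, relative reading: (b − f)/b ≥ 0.10 and b < 75.

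**3. Examples.** The protocol-text column shows only whether the fall and final-value conditions are met, leaving the lung-involvement limit aside.

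| b to f | Protocol text: fall and final < 65 | Table 4 | SAP absolute | SAP relative |
|---|---|---|---|---|
| 50 to 40 | yes | yes | yes | yes |
| 74 to 64 | yes | yes | yes | yes |
| 75 to 64 | yes | yes | no | no |
| 78 to 60 | yes | yes | no | no |
| 90 to 45 | yes | yes | no | no |
| 100 to 50 | yes | yes | no | no |
| 75 to 65 | no | yes | no | no |
| 90 to 80 | no | yes | no | no |
| 74 to 66 | no | no | no | yes |
| 50 to 45 | no | no | no | yes |

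**4. Full comparison.** I took integer values with b from 30 to 120 and f from 20 to b.
- For b < 75, the absolute SAP reading and the protocol text agree on every pair.
- For b ≥ 75, the SAP flags none. The final < 65 condition flags 46 baselines (75 to 120) × 45 follow-up values (20 to 64) = 2070 pairs. Table 4 flags 3151, the sum of (b − 29) over b = 75 to 120.
- On the relative reading, the SAP also flags 195 pairs below 75 that meet neither protocol rule.

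These are counts of grid points. They are not patient frequencies.

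**5. Which branch applies.** Pulmonary function testing is mandatory (Protocol 9.2) and scheduled at V1, weeks 6 and 14, and months 6, 9 and 12. The FEV1 branch is therefore the normal one. The two branches also conflict: a symptom rise from 0 to 2 counts if FEV1 is missing, but the same rise with a measured fall from 90 to 45 does not.

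**6. Size per case.** One reclassified patient moves a FAS proportion by 1/N: 1/24 = 4.2 points, or 1/21 = 4.8 points. The FAS requires a completed first cycle and a week 6 assessment, so N may be below 24. For Kaplan-Meier estimates the shift depends on the number at risk at the time of the event.

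**The case against.** The strongest reply is that the SAP codes the protocol's own restriction. The protocol sentence is limited to patients with lung involvement and gives initial FEV1 < 75% as what establishes that involvement. On that reading, with an absolute fall, the two rules are identical. This stands as far as it goes, so a reader who infers that the SAP plainly contradicts the protocol text in 7.3.2.1 and 9.3 goes further than the documents allow.

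It does not rescue the rule, for three reasons:
- Table 4 has no such restriction, and the SAP adopts Table 4 in its primary-endpoint section.
- SAP 17.1 and 11.4.2.1 expressly extend progression to organs not involved at V1.
- Appendix 2 scores FEV1 of 75-79% as lung score 1, yet the SAP exempts those patients.

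The protocol's symptom fallback also excludes only the change from 0 to 1, which suggests that lungs scored 0 are within its scope. That is an indication and does not settle the matter.

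The condition could also be defended as protection against non-specific falls from normal values. The algorithm already handles this: an organ whose abnormality is wholly explained by a documented non-GvHD cause is not classified at that visit.

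**Conclusion.** The defect stands. With FEV1 measured, SAP 17.1 cannot classify any patient with baseline FEV1 ≥ 75% as a lung progressor, contrary to Table 4 and to the SAP's own statements on uninvolved organs. On the absolute reading the error runs one way: it hides progression, leaves partial responses standing and removes progression events. If the 10% is relative, the rule also adds events that neither protocol rule recognises, so the one-way claim rests on the absolute reading.

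Three stronger inferences are not supported:
- New lung involvement is not missed in every case. When FEV1 is missing, a symptom rise from 0 to 2 or from 1 to 2 counts whatever the baseline FEV1.
- The primary result is not driven by this rule. The affected outputs are progression-free survival as derived in SAP 11.4.2.2 b, response by organ, and sensitivity analyses b and d.
- The documents do not establish final FEV1 < 65% for all patients as the protocol's rule. That would combine the threshold of the text with the scope of Table 4, and these two sources disagree with each other (90 to 80 counts only in Table 4).

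Each missed case is worth 1/N of the FAS, at least 4.2 points for N ≤ 24. How many patients start at 75% or above is not stated, so the total effect cannot be given.

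**What to change.** Before analysis, reconcile Protocol 7.3.2.1 and 9.3, Table 4 (with its copies in SAP 8.2.1 and 17.1) and the two statements in SAP 17.1 into one lung-progression rule. The rule should:
- drop the V1 < 75% condition, so that progression is assessed whatever the V1 involvement, as SAP 17.1 and 11.4.2.1 already state;
- define the fall as at least 10 absolute points of % predicted, which the protocol text and Table 4 share;
- state whether the protocol's final < 65% condition or Table 4's unrestricted 10-point fall applies, and report the other as a sensitivity analysis.

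The cost is one line of SAP text and code plus one additional run. FEV1 is already scheduled at baseline and at every response visit, so no new data are needed.

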8.2.2 Secondary endpoints

- OS is defined as the time from first infusion of ATO to death, regardless of the cause
- FFS is defined as related death, progression, or initiation of a new systemic treatment for chronic GvHD
- PFS is defined as survival with no evidence of relapse or progression of the original disease

- Corticosteroids dosage and percentage of reduction in corticosteroids dosage at 6 and 12 months after diagnosis of chronic GvHD and treatment with ATO as first line treatment
- Quality of life parameters using FACT-BMT and Lee Symptom Scale scores at 6 and 14 weeks, 6, 9 and 12 months after first infusion of ATO
- Tolerability and safety of ATO

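### SAP 17.1 counts mixed responders as Global progressive disease, contrary to the protocol's definition, and SAP 11.4.2.2 b) then counts them as PFS events

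*SAP*

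**What the plan says.** **Protocol.** Section 9.3 defines progressive disease as "at least one organ system has worsened by at least one stage without improvement of any other organ systems from baseline". The same definition appears in 7.3.2.1 and again in 11.3.1. A patient with both improvement and progression is classed separately: "Mixed response is defined as CR or PR in at least one organ accompanied by progression in another organ".

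**SAP 17.1.** The algorithm states that its rules are based on the protocol and a cited article on response measurement. At patient level it gives three rules:

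- The rule for worsening reads "Global progressive disease : si au moins un site avec une progression".
- Improvement that comes with no worsening at another site counts as a global PR: "au moins une réponse partielle sur un organe et avec une absence de progression pour un autre site".
- Patients who show both at once have a separate line: "Mixed response: si Progressive disease sur au moins un organe et Partial response sur au moins un autre".

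Organ-level progression is subject to thresholds. For skin, eyes, oesophagus and upper and lower GI the rule is "augmentation 1 point ou plus sur échelle de 0 à 3 = progression SAUF si changement de 0 à 1". Mouth, liver, lung and joints have their own thresholds.

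**Use in the SAP.** In 11.4.2.2 b) the PFS event is "Global progressive disease as define in Appendix 17.1", evaluated at M6 and M12. SAP 8.2.2, however, says "PFS is defined as survival with no evidence of relapse or progression of the original disease".

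**The concern.** The SAP omits one of the protocol's two conditions for progressive disease. A patient who improves in several organs and progresses in one is a mixed responder under the protocol. Under SAP 17.1 the same patient meets Global PD and, where the improvement is a PR, mixed response as well. The labels overlap and the SAP does not say which takes precedence.

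The SAP's mixed-response line is also narrower than the protocol's, because it names PR only. An organ in CR with progression elsewhere is mixed under the protocol. Under the SAP it may be Global PD alone, depending on whether an organ in CR is also flagged as PR. The liver rule in 17.1 treats the two as alternatives.

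At stake are the planned PFS tables and Kaplan-Meier plots at M6 and M12, in the FAS and PP populations. They would count as progression some patients whom the protocol does not class as progressive.

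**Working it through.** **1. The two rules as logic.** Give each organ one state: CR, PR, unchanged or PD.

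| Label | Protocol | SAP 17.1 |
|---|---|---|
| Global PD | some organ PD, no organ CR or PR | some organ PD |
| Mixed | some organ PD, another CR or PR | some organ PD, another PR |

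**2. Counting patterns for k organs.**

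- SAP Global PD: 4^k − 3^k
- Protocol PD (every organ unchanged or PD, at least one PD): 2^k − 1
- Protocol mixed: the difference, 4^k − 3^k − 2^k + 1
- SAP mixed (at least one PD and at least one PR): 4^k − 2·3^k + 2^k

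| k | All patterns | SAP Global PD | Protocol PD | Protocol mixed | SAP mixed | Protocol mixed, not SAP mixed |
|---|---|---|---|---|---|---|
| 2 | 16 | 7 | 3 | 4 | 2 | 2 |
| 3 | 64 | 37 | 7 | 30 | 18 | 12 |
| 7 | 16384 | 14197 | 127 | 14070 | 12138 | 1932 |

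Every protocol-mixed pattern is SAP Global PD, and every disagreement between the two PD rules is a mixed pattern. The last column holds the patterns with CR but no PR alongside progression, if an organ in CR is not also counted as PR. These counts show direction only; they are not probabilities.

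**3. Where Global PD is used.**

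- The main analysis (SAP 11.4.1.1) uses the investigator's judgement of CR or PR.
- The computed-response sensitivity tables report CR and PR only, and computed Global PR already excludes progression at another site.
- The by-organ table (11.4.2.1) uses organ-level progression.
- No table of Global PD against mixed response is planned.
- That leaves the PFS analyses in 11.4.2.2 b).

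**4. Size per patient.** The number of mixed responders is not given, so I assume 1 to 3 with no other event in the window.

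- Of 24 analysed: 1/24 = 4.2 and 3/24 = 12.5 percentage points on the crude event proportion.
- Of 21 analysed: 1/21 = 4.8 and 3/21 = 14.3 percentage points.

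**5. Why a modelled percentage is not reliable here.** Assume 9 independent sites with k involved. Each involved organ improves with probability p. A non-improving involved organ progresses with probability q, and an uninvolved site with probability u.

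- SAP PD = 1 − (1 − (1−p)q)^k (1−u)^(9−k)
- Protocol PD = (1−p)^k [1 − (1−q)^k (1−u)^(9−k)]

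With k = 3, p = 0.5 and q = 0.05:

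| u | SAP PD | Protocol PD | Share of SAP PD that is mixed |
|---|---|---|---|
| 0.05 | 1 − 0.975³ × 0.95⁶ = 31.87% | 0.125 × (1 − 0.95⁹) = 4.62% | 85.5% |
| 0.01 | 1 − 0.975³ × 0.99⁶ = 12.74% | 0.125 × (1 − 0.95³ × 0.99⁶) = 2.41% | 81.1% |
| 0 | 1 − 0.975³ = 7.31% | 0.125 × (1 − 0.95³) = 1.78% | 75.6% |

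With u = q, p from 0.3 to 0.6, q from 0.02 to 0.10 and k from 2 to 4, the mixed share runs from 48% to 97%. None of these inputs comes from the documents.

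**The case against.** The strongest counter-case has four parts.

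- **Reach.** Only a descriptive secondary endpoint is touched, with no test attached. This stands. A reader might infer that the primary endpoint or the computed response rate is biased. It is not: a mixed responder is a non-responder under either rule, and the main analysis does not use the algorithm.
- **Wrong event in any case.** The protocol lists PFS but does not define it by cGvHD progression, and SAP 8.2.2 ties it to the original disease. This also stands. A reader might infer that the fault lies only in the progression rule and that correcting 17.1 repairs PFS. It would not; the event in 11.4.2.2 b) has to be settled too. If it is settled as in 8.2.2, Global PD leaves the PFS curve, but the overlapping labels in 17.1 remain.
- **Conservatism.** Counting any organ progression can only lower the curve, which is the cautious direction in a single-arm study. That could be a legitimate choice, but the SAP does not declare or justify it as a departure. It presents 17.1 as based on the protocol, although it does flag a liver-score rule as absent from its source article.
- **Overreading.** Two stronger statements are tempting. One is that any single-organ worsening counts as progression. It does not: the organ thresholds apply, and a change from 0 to 1 is excluded for skin, eyes and the GI scores. The other is that most SAP progressions would be mixed responders. That rests on a model with invented inputs. Lowering the progression probability at uninvolved sites, which the thresholds make plausible, moves the modelled SAP PD rate from about 32% to about 7%.

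**Conclusion.** The point holds as a conflict of definitions. SAP 17.1 drops the protocol's no-improvement condition, so Global PD contains every protocol PD patient plus every mixed responder, with no precedence rule. SAP 11.4.2.2 b) carries that into PFS at M6 and M12. The direction is certain: for cGvHD progression, the event count can only equal or exceed the count under the protocol's definition. The size is unknown. The one figure that follows from the planned sample is about 4.2 percentage points on the crude event proportion per mixed responder. It assumes that 24 patients are analysed and that the patient has no other event; it is larger if fewer are analysed. The fault should be corrected before the analysis, but it does not threaten the trial's main conclusion.

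**What to change.** In SAP 17.1:

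1. Define Global PD as progression, by the existing organ thresholds, in at least one site and no CR or PR in any other organ.
2. Define mixed response as CR or PR in at least one organ with progression in another. If CR is not added, a patient with CR in one organ and progression in another could fall into neither category once step 1 is made.
3. State that the patient-level categories are mutually exclusive.

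In SAP 11.4.2.2 b), reconcile the PFS event with 8.2.2. If a cGvHD progression curve is kept, label it as such and use the protocol's PD definition. If the broader rule is preferred, declare and justify it as a departure from the protocol.

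**Cost.** A few lines of text and the matching program conditions; no new data, and no change to the response rates. The downside is that mixed responders leave the event set despite documented organ progression, so the curve becomes more favourable. Report the number of mixed responders at M6 and M12 alongside it.
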